## **2. Objective**

The objective of this study is to determine if a SPG block performed after concussion is associated with improvements in post-traumatic headache. The primary outcome will be measured by a reduction in headache severity score of 50% or more in the 48 hours following the procedure compared to the 48 hours prior to the procedure. Secondary objectives will be measured by a reduction in Patient Global Impression of Change rating, number of headache occurrences, days with headache, hours per day with headache, and as-needed headache medication uses. Exploratory objectives are to evaluate if a SPG block improves other non-headache concussion symptoms, as measured by Sport Concussion Assessment Tool version 5 (SCAT5) symptom numbers and severity scores at baseline prior to the procedure and following the procedure; and to evaluate if a SPG block results in improvement in physiologic changes related to potential autonomic nervous system dysfunction due to concussion, as measured by comparisons in orthostatic heart rates and resting heart rate variability recorded prior to and after the procedure.

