## **A Phase II Randomized Controlled Double-Blind Clinical Trial of Sphenopalatine Ganglion Block for Headache after Concussion**

Specific Aim #2: To evaluate the effects of a SPG block on headache frequency and duration after concussion. We hypothesize that patients who receive a SPG block with lidocaine will report less headache days, less headache episodes, and a lower mean number of hours with headache per day than the patients who receive a placebo SPG block in the one week after the SPG block compared to the one week before the SPG block.

Specific Aim #3: To evaluate the effects of a SPG block on as-needed headache treatments after concussion. We hypothesize that patients who receive a SPG block with lidocaine will report a lower mean number of doses of as-needed headache treatments per day than the patients who receive a placebo SPG block in the 48 hours and one week after the SPG block compared to the 48 hours and one week before the SPG block.

Exploratory Aim #1: To evaluate the effects of a SPG block on non-headache concussion symptoms. We hypothesize that patients who receive a SPG block with lidocaine will report lower symptom scores for nausea or vomiting, dizziness, blurred vision, sensitivity to light, and sensitivity to noise than those who receive a placebo SPG block in the 24 hours, 48 hours and one week after the SPG block compared to the 24 hours, 48 hours, and one week before the SPG block.

Exploratory Aim #2: To explore the potential effects of a SPG block on heart rate measurements. We hypothesize those receiving a SPG block with lidocaine will have lower rates of abnormal orthostatic heart rate elevations on standing and higher RMSSD (root-mean square differences of successive R-R intervals) than those who receive a placebo SPG block at 15 minutes following the SPG block compared to before the SPG block.

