#### *6.3 Participants:*

Participants in this study will include patients between 18 and 60 years of age who have been diagnosed with a concussion. Participants will be randomized into one of two groups:

1. Treatment: participants in this group will receive a SPG block using an aqueous 1% lidocaine solution.
2. Control: participants in this group will receive an identical placebo SPG block using a normal saline solution.

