### ***8. Statistical Design***

## **A Phase II Randomized Controlled Double-Blind Clinical Trial of Sphenopalatine Ganglion Block for Headache after Concussion**

For the primary outcome, an analysis of covariance (ANCOVA) model will be used to determine treatment effect. The post-treatment headache severity score will be the dependent variable, and the pre-treatment headache severity score and treatment type (lidocaine or placebo) will be independent variables in the model. An ANCOVA model will be used to evaluate for treatment effect in post- vs pre-treatment mean headache severity scores in the 48 hours following the SPG block compared to the 48 hours before the SPG block.

Similar ANCOVA models also will be used to evaluate for between-group treatment effect for the following secondary and exploratory outcomes:

- mean number of days with headache in the one week post-SPG block compared to one week pre-SPG block.
- mean number of headache occurrences within both 48 hours pre- and post-SPG block and one week pre- and post-SPG block
- mean number of headache hours per day within both 48 hours pre- and post-SPG block and one week pre- and post-SPG block
- mean number of as-needed headache treatment uses per day within both 48 hours pre- and post-SPG block and one week pre- and post-SPG block
- mean symptom severity scores in all 22 symptoms on the SCAT5 symptom checklist in both the 48 hours and one week pre-SPG block compared to 48 hours and one week post-SPG block
- mean orthostatic heart rate on standing, and mean orthostatic heart rate change from supine to standing, post-SPG block compared to pre-SPG block
- root mean square of successive differences (RMSSD) post-SPG block compared to pre-SPG block

For the following secondary outcomes, a mixed design analysis of variance (ANOVA) will be used, with a within-subjects factor of time (e.g. pre- vs post-SPG block) and a between-subjects factor of treatment (SPG block with lidocaine vs SPG block with saline):

- mean headache severity score within 15 minutes, 2 hours, 24 hours, and one week post-SPG block compared to immediately prior to procedure, 24 hours, and one week pre-SPG block.
- values on the PGIC rating scale at 2 hours and 24 hours post-procedure in those who received an SPG block with lidocaine compared to a placebo SPG block

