For post-hoc analyses, an independent samples t-test (for normal distributions) or Wilcoxon rank-sum test (for non-normal distributions) will be used to compare mean differences, and chi-square tests (for normal distributions) or McNemar's tests (for non-normal distributions) will be used to compare proportional differences.

Participant characteristics will be reported by treatment group, and these will be evaluated for any differences between groups in any characteristic variables, including age, sex, baseline history of migraine, baseline history of depression or anxiety, baseline history of ADHD, previous history of concussions, and referral for cervical and/or vestibular physical therapy. If any differences in these

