## **A Phase II Randomized Controlled Double-Blind Clinical Trial of Sphenopalatine Ganglion Block for Headache after Concussion**

characteristics exist between-groups, they will be adjusted for in the analysis as independent variables in the ANCOVA model.

To control for multiple comparisons, a false discovery rate (FDR) will be used. In the event of missing data due to participant withdrawal from study or failure to complete all online survey data, we will use multiple imputation to estimate the missing values. All statistical analyses will be performed using SPSS (IBM, Armonk, NY).

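### The rule for post-hoc comparisons of proportions chooses between chi-square and McNemar's test by normality, which a yes/no outcome does not have; McNemar's test is invalid between the two independent arms.

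*Combined protocol and SAP*

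**What the plan says.** Section 8 (Statistical Design) gives one sentence on post-hoc tests. For means it reads "For post-hoc analyses, an independent samples t-test (for normal distributions) or Wilcoxon rank-sum test (for non-normal distributions"), and for proportions "chi-square tests (for normal distributions) or McNemar's tests (for non-normal distributions) will be used to compare proportional differences". It does not say which proportions are meant, or whether the comparison is between arms or before versus after the block.

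Other places bear on how the sentence would be used:

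- **Design (Section 6.3).** "Participants will be randomized into one of two groups". Section 6.14 adds block randomisation to equal group sizes. No matching or crossover is described.
- **Primary analysis (Section 8).** "For the primary outcome, an analysis of covariance (ANCOVA) model will be used to determine treatment effect". This is a model for the severity score, not for a proportion.
- **Yes/no quantities elsewhere.** Section 2 states the primary outcome as "a reduction in headache severity score of 50% or more". Exploratory Aim #2 (Section 3) expects "lower rates of abnormal orthostatic heart rate elevations on standing" with lidocaine. Section 8 says of participant characteristics, several of them binary, that "these will be evaluated for any differences between groups in any characteristic variables", and that where differences exist "they will be adjusted for in the analysis as independent variables in the ANCOVA model".

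The ANCOVA and mixed-ANOVA lists in Section 8 contain no analysis of a proportion. The post-hoc sentence is therefore the only rule the plan offers for one.

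**The concern.** The selection criterion is the wrong kind of criterion. A binary outcome is Bernoulli, so normal versus non-normal does not describe it. Pearson's chi-square compares proportions in independent groups. McNemar's test compares two proportions measured on the same, or individually matched, subjects, and uses only the discordant pairs. Between lidocaine and saline there are no pairs, so the discordant counts are undefined.

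An analyst who judged the data non-normal and followed the text for a treatment comparison would have two ways to proceed, both wrong:

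1. Pair unrelated patients across arms, for example by order of enrolment. The p-value then depends on an arbitrary choice.
2. Feed the arm-by-response table to the McNemar routine. This tests a hypothesis other than equal response rates.

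If the same rule were carried over to the binary baseline characteristics, a spurious difference would add a covariate to the ANCOVA in a trial of 24 people.

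**Working it through.** **Inputs.** From the plan: 12 per arm and alpha 0.05 (Section 6.13). The plan gives no response rates and does not say whether tests are two-sided, so two-sided testing and every count and rate below are assumptions for illustration. The plan states no figure of its own on this point to reproduce.

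**Formulas.** Let x and y be the responders out of n = 12 in the two arms.

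- Pearson chi-square (uncorrected), 1 df: X² = ((x − y)/n)² / [p(1 − p)(2/n)], with p = (x + y)/(2n).
- Exact McNemar with discordant counts b and c: p = 2·P(Bin(b + c, ½) ≤ min(b, c)), capped at 1.
- Boschloo: Fisher's p-value used as the test statistic, with its tail probability maximised over the common response rate.

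**Step 1: one data set, 9/12 versus 3/12.** Chi-square: p = 12/24 = 0.5, so X² = 0.25/(0.25 × 0.1667) = 6.0 and the p-value is 0.014. Boschloo gives 0.023 and Fisher 0.039. Each unpaired test gives a single answer.

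For McNemar on arbitrary pairs, let k be the number of pairs in which both members respond. Then b = 9 − k and c = 3 − k:

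| k | b | c | exact McNemar p |
|---|---|---|---|
| 0 | 9 | 3 | 0.146 |
| 1 | 8 | 2 | 0.109 |
| 2 | 7 | 1 | 0.070 |
| 3 | 6 | 0 | 0.031 |

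The data are the same in every row; only the pairing differs.

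On the arm-by-response table the off-diagonal cells are 12 − x = 3 and y = 3, so p = 1.0 despite a 50-point difference.

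**Step 2: no difference, 2/12 versus 2/12.** On the arm-by-response table the off-diagonal cells are 10 and 2, so p = 2 × (1 + 12 + 66)/4096 = 0.039. Identical arms come out as significant.

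**Step 3: operating characteristics.** These are exact enumerations at 12 per arm, two-sided 0.05. The first three columns are type I error at equal true rates; the last is power.

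| Test | rate 0.2 | rate 0.3 | rate 0.5 | power, 75% vs 20% |
|---|---|---|---|---|
| Chi-square | 0.039 | 0.049 | 0.064 | 0.85 |
| Boschloo | 0.038 | 0.045 | 0.038 | 0.77 |
| Fisher | 0.012 | 0.017 | 0.023 | 0.72 |
| McNemar, arbitrary pairs, exact | 0.004 | 0.009 | 0.014 | 0.61 |
| McNemar, arbitrary pairs, asymptotic | 0.045 | 0.051 | 0.048 | 0.75 |
| McNemar on arm-by-response table, exact | 0.43 | 0.11 | 0.002 | below 0.01 |

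The two misuses fail differently. Arbitrary pairing does not inflate false positives to any extent; it loses power and gives a p-value that is not unique. The arm-by-response table can be grossly anti-conservative when response is uncommon, and has almost no power in the example.

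**The case against.** The strongest reply concerns reach. The sentence covers post-hoc analyses only. Section 8 gives the primary outcome an ANCOVA on the score and analyses orthostatic heart rate as means, so no listed analysis depends on this rule. The text never says that McNemar's test will be used between arms; the author may have had before/after data in mind, where it is valid, and attached the wrong label. The baseline paragraph names no test, so harm through covariate selection needs several further steps. The 43% and 11% rejection rates belong to a crude misuse that nothing in the plan suggests. Setting asymptotic chi-square (0.85) against exact McNemar (0.61) also overstates the loss: like for like, asymptotic McNemar on arbitrary pairs reaches 0.75, about 0.10 lower.

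Most of this stands as a limit on size. The primary analysis is untouched, between-arm use is an inference, the arm-by-response figures are a worst case, and under exact pairing a false baseline difference is less likely than with chi-square.

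None of it rescues the rule. Even if only before/after comparisons were intended, normality would not select McNemar's test, and chi-square would then be the wrong alternative. The means tests in the same sentence are both for independent groups, which makes the between-arm reading the natural one. An analyst who quietly substituted the right test would be departing from the written plan.

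**Conclusion.** The concern holds. The rule is wrong as written, and nothing elsewhere in the document corrects it. Its scope is any post-hoc comparison of a proportion. It would matter most if the 50% reduction outcome, the rate of abnormal orthostatic rise or the binary baseline characteristics were compared as proportions, because no other rule is given. It does not threaten the primary ANCOVA.

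The main consequence is a treatment p-value that is arbitrary (0.031 to 0.146 for one assumed data set), with a power loss of about 0.10 to 0.24 against chi-square at the assumed 75% versus 20% (0.85 − 0.75 and 0.85 − 0.61). Severe false-positive inflation arises only if McNemar's test is run on the arm-by-response table. The fault in the criterion rests on no assumption; the size rests on the assumed counts and rates and on the inferred between-arm use. It should be corrected before analysis.

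**What to change.** Replace the proportions half of the post-hoc sentence in Section 8 with wording such as: *Proportions are compared between arms by one unpaired test named in advance, with the risk difference and a 95% confidence interval. McNemar's test is used only for within-person change from before to after the block, never for the treatment comparison.* Delete the normality criterion for proportions, and state which outcomes the rule covers, including whether it applies to the binary baseline characteristics.

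The cost is one sentence, with no change to design, sample size or data collection. The choice of unpaired test is a trade-off at 12 per arm. Fisher's test is conservative (type I error at most 0.023) and gives up power. Uncorrected chi-square has the most power in the example but its size reaches 0.064. Boschloo's test keeps size at or below 0.045 with intermediate power. Any of them is acceptable if named beforehand; confirm that the chosen one can be run in SPSS, the software named in Section 8.

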## **A Phase II Randomized Controlled Double-Blind Clinical Trial of Sphenopalatine Ganglion Block for Headache after Concussion**

characteristics exist between-groups, they will be adjusted for in the analysis as independent variables in the ANCOVA model.

To control for multiple comparisons, a false discovery rate (FDR) will be used. In the event of missing data due to participant withdrawal from study or failure to complete all online survey data, we will use multiple imputation to estimate the missing values. All statistical analyses will be performed using SPSS (IBM, Armonk, NY).

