## A Phase II Randomized Controlled Double-Blind Clinical Trial of Sphenopalatine Ganglion Block for Headache after Concussion

Potential participants who are eligible for the study will be identified from a concussion clinic at the University of Michigan and will complete the informed consent process. After enrolling in the study, they will be linked to a daily online survey which will ask them to record daily symptom severity scores using the Sport Concussion Assessment Tool version 5 (SCAT5) symptom checklist, rating symptoms (including headache) on a scale of 0 to 6, with 0 corresponding to “absent” and 6 corresponding to “severe.” They will also be asked to record the number of headache episodes, the number of hours with headache, and the number of doses of as-needed headache medication usage every 24 hours for the one week prior to the research visit.

Participants will take part in one in-person research visit, during which the SPG block procedure will be performed. At the beginning of the visit, participant demographic information and baseline characteristics will be recorded, including age, sex, height, weight, date of concussion, history of baseline migraine, depression, anxiety, or ADHD, and history of previous concussions. The participant also will complete the 22-item SCAT5 symptom checklist, as before. Participants will then be fitted with a chest-worn Polar heart rate monitor, which will record resting heart rate and R-R interval while in the supine position. Heart rate will then be recorded immediately after standing, and after standing for two minutes. Next, the SPG block procedure will be performed, as described below. 15 minutes after the procedure, heart rate and R-R interval will be recorded in identical fashion to the pre-procedure recordings. Finally, the participant will again complete the SCAT5 symptom checklist.

Following the research visit, they will record SCAT5 symptom scores, headache episodes, headache hours, and as-needed headache medication usage every 24 hours for the one week following the research visit, identical to the pre-procedure recordings. Additionally, they will complete the SCAT5 symptom checklist and rate their status on the PGIC scale at two hours post-SPG on the day of the research visit. Their direct participation in this study will conclude after the one week post-SPG block survey data is recorded.

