### *6.13 Sample size and power calculation:*

## **A Phase II Randomized Controlled Double-Blind Clinical Trial of Sphenopalatine Ganglion Block for Headache after Concussion**

Sample size calculations were based on previous studies on the use of SPG blocks in acute migraine headache[11] and chronic migraine,[5] in addition to considering the expected recruitment potential from the clinic in the one year study grant period. A sample size of 24 participants (12 per group) was calculated to achieve 80% power with an alpha cutoff 0.05.

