### ***6.14 Randomization***

To achieve two groups with equal numbers balanced by treatment type (i.e. SPG block with lidocaine vs placebo with saline), a block randomization method will be utilized. To maintain blinding, the study coordinator will prepare SPG block materials based on the randomization scheme in advance of the participant study visit.

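### The imbalance-triggered covariate rule has no threshold, cap or prognostic criterion, so the primary ANCOVA is not fixed until data are seen and can lose power

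*Combined protocol and SAP*

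**What the plan says.** Section 8 (Statistical Design) of the combined protocol and SAP defines the primary model clearly: post-treatment severity is the outcome, and "the pre-treatment headache severity score and treatment type (lidocaine or placebo) will be independent variables in the model".

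Later in Section 8 the characteristics are summarised by arm and "these will be evaluated for any differences between groups in any characteristic variables, including age, sex, baseline history of migraine". The rest of the list is depression or anxiety, ADHD, previous concussions, and referral for cervical or vestibular physical therapy: seven named items, introduced as examples. If differences in these "characteristics exist between-groups, they will be adjusted for in the analysis as independent variables in the ANCOVA model".

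Three nearby statements might be thought to define a difference, but none does:

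- The two-group tests are introduced with "For post-hoc analyses, an independent samples t-test (for normal distributions) or Wilcoxon rank-sum test". They serve post-hoc analyses and are not linked to the covariate rule.
- "To control for multiple comparisons, a false discovery rate (FDR) will be used" does not mention baseline comparisons.
- The only significance level in the plan is in Section 6.13: "A sample size of 24 participants (12 per group) was calculated to achieve 80% power with an alpha cutoff 0.05". That is the sample-size alpha, not a threshold for imbalance.

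**The concern.** A covariate helps an ANCOVA when it predicts the outcome. Chance imbalance on a covariate that does not predict the outcome has the opposite effect: adjusting for it inflates the variance of the treatment estimate and uses a degree of freedom. Allocation is randomised (Section 6.14), so any difference in a pre-allocation characteristic is chance. The rule therefore selects on the feature that costs precision and ignores the one that gains it.

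Because a difference is undefined, the covariate set is also unknown until the data are in. Several models comply with the text, and the plan does not say which is primary if they disagree. With 24 participants, that can decide the conclusion.

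Physical therapy referral raises a separate question. Section 6.10 does not name it among the items recorded at the visit, and nothing says that its value is settled before allocation. If it were settled afterwards, adjusting for it could bias the treatment effect.

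**Working it through.** **The plan's own figure.** Section 6.13 gives no effect size, SD, test or sidedness, so 24 participants cannot be reproduced, only back-solved. Two-sided alpha of 0.05 is assumed. The normal approximation, n = 2(1.96+0.842)²/d², returns 12 per arm at d = 1.14. The noncentral t with residual df 24−3 = 21 needs 1.1995 residual SD if baseline scores are exactly balanced. Allowing for chance baseline imbalance (variance factor 21/20) gives 1.1995×√1.05 = 1.229 residual SD, or 1.06 outcome SD at an assumed pre-post correlation of 0.5. This is the anchor for the simulation.

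**How often the rule fires.** With seven independent comparisons, 1−0.95⁷ = 0.302 at p<0.05 and 1−0.80⁷ = 0.790 at p<0.20. The simulated rates are about 31% and 79%.

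**Analytic cost of covariates that predict nothing.** Take 1.1995 residual SD as 80% power. Adding k covariates gives df = 21−k and an average variance factor of 21/(21−k):

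- k = 1: factor 1.05, power 78%
- k = 2: factor 1.105, power 76%
- k = 7: df 14, factor 1.50, power 61%

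A covariate selected because it is imbalanced costs more. At exactly p = 0.05 (t = 2.074, df 22), its R² with treatment is 4.301/(4.301+22) = 0.164. The variance factor is 1/(1−0.164) = 1.20, and power falls to 72% with one such covariate.

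**Simulation** (20,000 replicates per scenario; Monte Carlo error about 0.3 points for power and 0.15 under no effect). Assumed, independent characteristics: age normal; previous concussions Poisson with mean 1; sex 50%, migraine 30%, depression or anxiety 35%, ADHD 15%, referral 40%. Screening is by t-test or chi-square. Scenarios give the share of remaining outcome variance explained. Entries are power, %.

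| Scenario | Base model | Screen p<0.05 | Screen p<0.20 | All seven | One prespecified (migraine) |
|---|---|---|---|---|---|
| A: none prognostic | 80.3 | 76.5 | 71.4 | 61.1 | 78.3 |
| B: one at 10% | 80.2 | 76.9 | 72.6 | 65.5 | 82.2 |
| C: one at 20% | 80.2 | 77.4 | 73.9 | 70.7 | 86.4 |
| D: two at 10% | 80.3 | 77.1 | 73.6 | 70.7 | 82.3 |
| E: seven at 5% | 80.3 | 78.0 | 75.7 | 79.1 | 80.1 |
| F: three at 20/15/10% | 80.3 | 78.2 | 77.5 | 85.0 | 86.3 |
| G: seven at 8% | 80.3 | 79.0 | 79.0 | 91.2 | 81.4 |

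In the trials where the p<0.05 rule fires, its power is 68-73%, against 77-80% for the base model in the same trials.

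**Other effect sizes** (10,000 replicates; scenarios A, E, F). At 0.8 outcome SD (base power 56-57%), screening at p<0.05 loses 2.9-3.6 points and at p<0.20 loses 5.0-7.8. At 1.0 SD (base 75-76%), the losses are 2.2-3.4 and 4.0-8.4.

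**Disagreement and error rate.** The three readings (p<0.05, p<0.20, all seven) differ on significance in 22-24% of trials; p<0.05 and p<0.20 differ in 8-11%. Under no effect, each single reading is significant in about 3-5% of trials. At least one of the three is significant in about 8%, or 9-10% if the base model also counts.

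**The case against.** The strongest reply is that the harm is small on conventional readings:

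- At p<0.05 the loss is only 1-4 points.
- With Fisher's exact test for the binary items, about 17% of trials are flagged and the loss is about 1-2.5 points. Fisher is a natural choice here: on the assumed prevalences, four of the five binary items have expected counts below 5 per arm (12×0.15 = 1.8 up to 12×0.40 = 4.8).
- If the FDR were applied to the seven comparisons, about 4% of trials would be flagged and under 1 point lost.
- The larger figures for disagreement and false positives depend on counting all seven as a compliant reading. If the choice is only between p<0.05 and p<0.20, the false-positive rate is 4.6-6.4%. Any inflation also supposes an analyst who chooses after seeing results, whereas the rule refers to baseline characteristics.
- Losing power is not inevitable. Outside the grid above, with each of the seven explaining 10-12% of variance, screening at p<0.20 gained 1-2 points.
- Recording age, sex and history at the visit, after materials are prepared, is no defect, because allocation cannot alter them. The Section 6.10 list is itself open-ended, so the absence of referral from it proves little.

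Most of this stands as a limit on size. It does not supply the missing definition: the plan chooses none of these readings. Nor is the near-full model far-fetched, since the text refers to any difference. In a separate run of 4,000 trials with the effect set at 1.20 residual SD and no prognostic characteristic, a standardised difference above 0.1 added 5.8 of seven characteristics on average, with 62% power. On referral, only confirmation of timing is needed.

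**Conclusion.** The concern holds. The rule leaves the primary covariate set open until data are seen. Screening on imbalance lost power against the plan's own base model in all seven scenarios tabulated: 1-4 points at p<0.05 and 1-9 at p<0.20. Entering all seven loses 19 points if none is prognostic, 10-15 if one explains 10-20%, and about 1 if each explains 5%; it gains 5-11 if several are strongly prognostic. The documents do not say which case applies.

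Type I error is not inflated by any one reading applied mechanically. The risk lies in choosing among compliant readings once results are known.

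The magnitudes rest on a back-solved effect size and on assumed prevalences, independence and prognostic strengths, so they indicate direction and rough size only. This is a correction worth making before analysis, not a fatal flaw.

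**What to change.** Delete the imbalance-triggered rule from Section 8 and state instead:

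- The primary model is treatment plus pre-treatment severity, with at most one or two further covariates that the investigators name as prognostic; otherwise none. Name them now if possible, and at the latest before unblinding.
- Baseline characteristics are reported descriptively by arm and play no part in choosing the model.
- Any other adjusted model is a sensitivity analysis, with its covariates listed before unblinding.
- Physical therapy referral is not adjusted for unless its value is determined before allocation.

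One prespecified covariate beats the p<0.05 rule by about 2 points if it is not prognostic (78.3 against 76.5) and by 5-9 points if it explains 10-20% (82.2 against 76.9; 86.4 against 77.4).

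The cost is SAP wording, with no new data. There are three downsides:

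- Chance imbalance outside the named covariates stays unadjusted in the primary result. When a prognostic characteristic is among those screened, the base model's false-positive rate in trials flagged at p<0.05 is 6-9%, although it remains 5% overall. The sensitivity analysis would show such cases.
- From 80% power, one covariate that proves non-prognostic costs about 2 points and two cost about 4.
- If several listed characteristics are strongly prognostic, the base model forgoes the 5-11 points that entering all seven could gain.
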